Subjects who received at least one and up to five prior lines of therapy will be initially enrolled to receive preladenant at 25 mg twice a day in monotherapy (Arm 1). Treatment allocation will be accomplished by non-random assignment. Enrollment in Arm 1 (preladenant in monotherapy) at DL2 (Dose Level 2) will begin once all subjects complete Cycle 1 at DL1 (Dose Level 1) of Arm 1 and a dose escalation decision has been made. Enrollment in Arm 2 (preladenant in combination with pembrolizumab) at DL1 will also begin once all subjects complete Cycle 1 at DL1 of Arm 1 and a dose escalation decision has been made. Thus, the starting dose of preladenant in the combination arm will generally be one level below the dose level being tested concurrently in the preladenant monotherapy arm.

Barring dose limiting toxicities (DLTs) during Cycle 1, additional subjects will be enrolled and dose-finding will proceed according to an algorithm based on the mTPI method, targeting a preladenant dose with a 30% DLT rate for each arm to determine the respective RP2D (see Section 5.2.1.2).

In Part 2, two expansion cohorts targeting a specific tumor type will enroll approximately 30 subjects each. Subjects with select advanced solid tumors who received at least one and up to five prior lines of therapy will be enrolled to further evaluate safety and efficacy of preladenant in combination with pembrolizumab at the RP2D defined in Part 1 Arm 2 (See Section 5.2.1.3).

Additional lower and/or higher doses of preladenant in combination with pembrolizumab may also be explored in Part 2, if they were previously assessed in Part 1, and were deemed generally safe and tolerable. The final RP2D for future studies will be confirmed using all available safety information (including early and late toxicities from Parts 1 and 2), as well as PK and PD data, and preliminary efficacy assessments.

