### **5.1.3 Subject Exclusion Criteria**

The subject must be excluded from participating in the trial if the subject:

1. Has disease that is suitable for local treatment administered with curative intent.
2. Has received previous treatment with an immunomodulatory agent (e.g. anti-PD-1/PD-L1 or anti-CTLA-4) and was discontinued from that treatment due to a Grade 3 or higher irAE.
3. Has received previous treatment with an A2a receptor antagonist (e.g. CPI-444; HTL1071; PBF-509).
4. Has had chemotherapy, definitive radiation, or biological cancer therapy within 4 weeks (2 weeks for palliative radiation) prior to the first dose of study therapy, or has not recovered to CTCAE grade 1 or better from any adverse events that were due to cancer therapeutics administered more than 4 weeks earlier (this includes subjects with previous immunomodulatory therapy with residual immune-related adverse events). Subjects receiving ongoing replacement hormone therapy for endocrine immune-related adverse events will not be excluded from participation in this study.
5. Is currently participating and receiving study therapy or has participated in a study of an investigational agent and has received study therapy or has used an investigational device within 28 days of administration of study therapy.

Note: Subjects who have entered the follow-up phase of an investigational study may participate as long as it has been 4 weeks since the last dose of the previous investigational agent.

6. Has taken during the 14 days prior to start of study treatment, or is currently taking drugs or grapefruit and star fruit in diet that interferes with CYP3A4 or CYP2C8 as listed in [Table 11](#).
7. Has taken during the 5 days prior to start of study treatment, or is currently taking Proton Pump Inhibitors (PPI).
8. Has a diagnosis of immunodeficiency or is receiving chronic systemic steroid therapy (exceeding 10 mg dose daily of prednisone equivalent) or any other form of immunosuppressive therapy within 7 days prior the first dose of trial drug.

9. Is expected to require any other form of systemic or localized antineoplastic therapy while in study.
10. Has a history of a second malignancy, unless potentially curative treatment has been completed with no evidence of malignancy for 5 years.

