Blood for Stimulation Assay 		X			X							
PBMC for Biomarker Analysis 	X			X 		X 						
Serum for Cytokine Analysis 		X			X		X					
Plasma Collection for Proteomic Analysis 		X	X	X	X		X					
Urinalysis 	X											
Chemistry 	X	X	X	X	X	X	X		X	X		

Preladenant in Monotherapy (Arm 1 ; Part 1)												
	Screening	Treatment Phase						Tumor Assessment	End of Treatment	Post-treatment Follow-Up Phase		
		Cycle 1			Cycle 2-4		Cycles 5 and all Subsequent Cycles	Every 9 weeks	Discontinuation	Safety Follow-up		Survival Follow-Up 
		Day 1	Day 8	Day 15	Day 1	Day 15	Day 1		At Treatment Discontinuation	30 days after the last dose	90 days after the last dose	Every 12 weeks post discontinuation
Scheduling Window (Days) 	-28 to -1	+3	±3	±3	±3	±3	±3	±7		+7	+7	±7
Prothrombin Time (PT)/International Normalized Ratio (INR) and Activated Partial Thromboplastin Time (aPTT) 	X											
Serum or Urine Pregnancy Test – if applicable 	X	X										
On-treatment Tumor Biopsy 					X							
Pharmacokinetics Evaluations												
Blood for preladenant PK assay 		X	X	X	X		X					

AE = adverse event; ALT = alanine aminotransferase; AST = aspartate aminotransferase; BUN = blood urea nitrogen; CR = complete response; CT = computed tomography; ECG = electrocardiogram; ECOG = Eastern Cooperative Oncology Group; min = minute; PGt = pharmacogenetic; PK = pharmacokinetic; PR = interval between the P wave and the QRS wave; QRS = interval from onset of the Q wave to end of the S wave; QT = interval from onset of the QRS complex to end of the T-wave; QTcF = QT interval corrected for heart rate; SAE = serious adverse event; SGOT = serum glutamic oxaloacetic transaminase; SGPT = serum glutamic pyruvic transaminase.

1. Visits should occur within the prespecified days window (e.g. +/- 3d).
2. Screening procedures to be performed within 28 days prior Cycle 1 Day1 (C1D1), unless otherwise noted. Informed consent may be obtained more than 28 days prior to C1D1 to allow for tumor tissue collection pre-treatment.
3. Subject Identification Card must be given to Subject at the start of study and must be collected when the Subject is no longer participating in any portion of the study.

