13. This blood sample will be drawn for planned analysis of the association between genetic variants in DNA and drug response. If the IRB/IEC does not approve of the planned analysis of the association between DNA variation and drug response, or if there is a local law or regulation prohibiting the same, data analysis will be limited. Leftover extracted DNA will be stored for future biomedical research if the subject signs the FBR consent.
14. Hematology tests include complete blood count with 5-part differential and platelets. Hematology does not need to be repeated on C1D1 if Screening samples were obtained within 3 days of C1D1.
15. Blood sample for RNA analysis should be obtained predose of administration of preladenant on Day 1 of Cycle 1, Cycle 2, Cycle 5 and at the Treatment Discontinuation Visit. Leftover extracted RNA will be stored for future biomedical research if the subject signs the FBR consent.
16. Procedures for collection of PD samples and precise time points are described in the Procedures Manual. Blood sample for Stimulation Assay should be obtained predose, 2hr and 4hr post-dose of administration of preladenant on Day1 of Cycle 1 and Cycle 2.
17. Procedures for collection of PD samples and precise time points are described in the Procedures Manual. PBMC samples for Biomarker Analysis should be obtained at screening, and predose of administration of preladenant on Day 15 of Cycle 1, Cycle 2 and Cycle 3.

18. Procedures for collection of PD samples and precise time points are described in the Procedures Manual. Serum Sample for cytokine analysis should be obtained at predose of administration of preladenant on Day 1 of each cycle for all treatment cycles.
19. Procedures for collection of PD samples and precise time points are described in the Procedures Manual. Plasma Collection for Proteomic Analysis should be obtained at each time point when preladenant PK samples are collected. Samples need to be obtained at pre-dose, 1 hour, 2 hours, 4 hours and 8 hours after drug administration of preladenant (+/- 10 minutes) on Day 1 of Cycle 1 and Cycle 2; Prior to dosing on Cycle 1 Day 8; Prior to dosing on Cycle 1 Day 15; Prior to dosing on Cycle 4 Day 1; And, Prior to dosing on Cycle 8 Day 1. If the sample day falls on a weekend or a holiday, please consult the Sponsor for alternate sample collection times.

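### The only pre-treatment PBMC sample is taken at screening, up to 28 days before first dose, while every other serial blood biomarker has a Cycle 1 Day 1 pre-dose baseline

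*Combined protocol and SAP*

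**What the plan says.** Section 6.1, Arm 1 footnote 17, states: "PBMC samples for Biomarker Analysis should be obtained at screening, and predose of administration of preladenant on Day 15 of Cycle 1", and continues with Day 15 of Cycles 2 and 3. Footnote 18 of the Arm 2 chart, which also serves Part 2 and cross-over subjects, is the same. In both charts the row "PBMC for Biomarker Analysis" is marked at Screening and on Day 15 visits, and is blank at C1D1.

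Footnote 2 of both charts sets the window: "Screening procedures to be performed within 28 days prior Cycle 1 Day1 (C1D1), unless otherwise noted". The hematology, chemistry and urinalysis rows carry footnote 5, which asks for testing within 3 days of Day 1. The PBMC row does not.

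The other serial blood biomarkers start on C1D1 before dosing. For cytokines: "Serum Sample for cytokine analysis should be obtained at predose of administration of preladenant on Day 1 of each cycle". The RNA, stimulation-assay and proteomic footnotes likewise give a C1D1 pre-dose draw.

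The washouts in Section 5.1.3 count back from first dose, not from the screening sample. Criterion 4 excludes a subject who "Has had chemotherapy, definitive radiation, or biological cancer therapy within 4 weeks (2 weeks for palliative radiation) prior to the first dose". Criterion 8 covers chronic systemic steroids above 10 mg prednisone equivalent or "any other form of immunosuppressive therapy within 7 days prior the first dose of trial drug".

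Section 2.1 says the final RP2D will be confirmed from all safety information, "as well as PK and PD data, and preliminary efficacy assessments". Sections 2.1 and 5.2.1.2 also let PD data inform whether lower or higher doses are explored.

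**The concern.** The trial has no untreated or pembrolizumab-alone arm, so the natural reading of serial PBMC data is within-subject change. That reading is cleanest when the reference sample immediately precedes the first dose. Here it may be four weeks old, it may sit at the start of washout, and its age can vary between subjects from 1 to 28 days, in dose cohorts of 3 to 14. Part of any change to C1D15 could then reflect what happened after prior therapy stopped.

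At stake is one exploratory PD readout that is among several inputs to dose exploration and RP2D confirmation. The timing has to be settled before dosing, because a pre-dose sample that was never drawn cannot be obtained later. No reason is given for treating PBMC differently from the other assays.

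**Working it through.** The plan states no figure on this point to reproduce. The check is day arithmetic, followed by a labelled illustration.

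**Inputs.** Screening sample at Day -s, with s from 1 to 28 (Section 6.1). C1D15 falls 14 days after C1D1, or 11 to 17 days with the ±3-day window. Washouts before first dose: 28 days for chemotherapy, biological therapy and definitive radiation, 14 days for palliative radiation, and a 7-day look-back for steroids and immunosuppressants (Section 5.1.3).

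**Share of the interval before any study drug** = s / (s + 14):

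| Screening sample | Interval to C1D15 | Untreated days | Share |
|---|---|---|---|
| Day -28 | 28 + 14 = 42 | 28 | 67% |
| Day -14 | 14 + 14 = 28 | 14 | 50% |
| Day -3 | 3 + 14 = 17 | 3 | 18% |
| Day -1 | 1 + 14 = 15 | 1 | 7% |

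With the C1D15 window, the Day -28 share runs from 28/45 = 62% to 28/39 = 72%.

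**Time since prior therapy.** Under the minimum 28-day washout, a Day -28 sample is 28 - 28 = 0 days after the last chemotherapy or biologic dose. The C1D15 sample is 28 + 14 = 42 days after it.

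**Illustration with zero drug effect (assumed, not from the documents).** Suppose a marker stands at a fraction d of its own usual level at Day -28 and recovers with half-time h: f(t) = 1 - (1 - d) × 2^(-t/h), with t in days from Day -28. Take d = 0.7 to 0.9 and h = 7, 14 or 28 days.

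- Day -28 baseline, f(42)/f(0) - 1. Largest (d = 0.7, h = 7): 0.9953/0.7 - 1 = 42.2%. Smallest (d = 0.9, h = 28): 0.9646/0.9 - 1 = 7.2%.
- C1D1 baseline, f(42)/f(28) - 1. Largest (d = 0.7, h = 28): 0.8939/0.85 - 1 = 5.2%. Smallest (d = 0.9, h = 7): 0.9984/0.9938 - 1 = 0.5%.
- Day -3 baseline, f(42)/f(25) - 1: 0.7% to 6.6%.

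Under this model nearly all the gain comes from removing a long gap. A baseline already within 3 days of first dose would do almost as well as C1D1.

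**The case against.** Four counter-arguments have weight.

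- **Treatment during screening.** A reader might infer from the washouts in Section 5.1.3 that immune-active therapy carries on through screening, so that PBMC is drawn on treatment. The documents do not support this. Section 5.5.2 bars systemic chemotherapy, biologics, most radiation and most systemic steroids during screening, and a 4-week washout spans the whole 28-day window, touching it only at Day -28. What stands is sampling soon after prior therapy ended, plus the permitted exceptions. On steroids, criterion 8 looks back only 7 days while Section 5.5.2 bars most use throughout screening; these passages must be reconciled.
- **The 3-day rule.** Section 7.1.5.1 requires laboratory tests within 3 days of first dose, and PBMC is listed among the laboratory procedures in the charts. If the rule covers PBMC, little is left of the concern. But the PBMC row lacks footnote 5, and Table 13 does not list PBMC, so the text is ambiguous.
- **No such analysis is defined.** A reader might infer that recovery will be counted as a preladenant effect. Nothing here says so: no PBMC endpoint, baseline or change analysis is given. Exploratory analyses are deferred to the sSAP, and precise PD times to the Procedures Manual, neither of which is available. In Arm 2 any change would belong to the combination.
- **Direction and weight.** Prior checkpoint inhibitors are allowed unless stopped for a Grade 3 or higher immune-related event, and their waning could push the other way. Dose escalation runs on DLTs, and the other PD assays have C1D1 baselines. Prior treatments are recorded, so analysis by time since therapy could help, as could comparisons among the Day 15 samples. None of these replaces a pre-dose sample.

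**Conclusion.** The scheduling gap is real. PBMC is the one serial blood biomarker without a C1D1 pre-dose baseline, and its only pre-treatment sample may be up to 28 days old and taken soon after prior therapy. Change to C1D15 could then mix the aftermath of that therapy with drug effect.

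The untreated share of the interval ranges from 7% (Day -1) to 67% (Day -28), and is at most 18% if the 3-day rule applies. The 7% to 42% apparent rise is a worst case in timing that rests on an assumed depression, half-time and upward recovery. It is not an estimate of bias in this trial, whose direction and size the documents cannot give.

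The consequence is confined to exploratory PD data that are one input to dose exploration and final RP2D confirmation. DLT rules and ORR are unaffected. This is a minor point, worth acting on because the remedy is cheap and must precede dosing.

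**What to change.** In Section 6.1, edit Arm 1 footnote 17, Arm 2 footnote 18 and both PBMC chart rows so that the baseline moves from Screening to pre-dose on Cycle 1 Day 1. Leave the Day 15 samples of Cycles 1 to 3 unchanged, and align the Procedures Manual. This also removes the doubt over whether the 3-day rule covers PBMC. State the PBMC baseline definition in the sSAP. Separately, reconcile criterion 8 of Section 5.1.3 with Section 5.5.2 on steroid use during screening.

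After the change the comparison with C1D15 spans 14 days (11 to 17), all on treatment. The number of PBMC samples per treated subject stays the same, and subjects who fail screening no longer give one.

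The cost is added blood volume at C1D1, which already carries genetic, RNA, stimulation, cytokine, proteomic, PK and safety draws. Section 7.1.3 leaves volumes to the Procedures Manual, so this burden cannot be checked here. The move reduces the problem without abolishing it: with minimum washout the new baseline lies 28 days after chemotherapy or biologics, and recovery may continue beyond that.
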